PROTOCOL

The components in this Supplementary Material document are as follows:

Part I: Research Plan

Part II: Modifications

Title: A Prospective Cohort Study of Exercise Rehabilitation in the Treatment of Parkinson's Disease

Place: Ruijin Hospital affiliated to Shanghai Jiao Tong University School of Medicine

Document Date: Jan. 1st, 2015

Modification Date: Modification 1 (Jan. 1st, 2016); Change 2: (Aug. 22nd, 2020)

Part I: Research Plan

Overview

We proposed to conduct a cohort study to observe whether Tai Chi intervention could delay the disease progression of Parkinson's disease (PD).

PD patients were enrolled into 5 Tai Chi classes which began at different timepoints from Jan. 2016 to Jan. 2019. Each participant was assessed before they joined the Tai Chi class. After the recruitment, they accepted continuous Tai Chi training in the classes till the last follow-up. We performed three times of follow-up in Nov. – Dec. 2019, Oct. - Nov. 2020 and Jun. – July 2021. Using propensity score matching, we matched PD patients who did not receive Tai Chi training as control group in gender, disease duration, age, and Hoehn – Yahr staging. The aim is to observe the effect of Tai Chi on delaying the disease progression of PD. This original study is registered at Chinese Clinical Trial Registry (Registration No.: ChiCTR2000036306; Registration date: August 22, 2020).

1. Participants

We recruited PD patients aged 50-80 years with Hoehn -Yahr stage 1-2.5. The medication was stable at least 3 months before recruiting and not changed during follow-up unless increasing antiparkinsonian drugs or the need of deep brain stimulation (DBS) is required according to the disease severity. PD was diagnosed by senior movement disorder specialists ([name], [name]) based on diagnostic criteria brought up by United Kingdom Brain Bank diagnostic criteria and MDS diagnostic criteria of PD in 2015 ^{1,2}. Patients who fitted any following item were excluded:

- 1) Secondary causes, such as inflammatory, drug-induced, vascular and toxin-induced parkinsonism.
- 2) Parkinsonism with other neurodegenerative diseases, such as progressive supranuclear palsy, multiple system atrophy, cortical basal ganglia degeneration, Wilson's disease.
- 3) Other neurological diseases, such as stroke.
- 4) Patients who were receiving any other clinical trials or regular exercise protocols.

- 5) Patients who had fall incidents in the 6 months before recruiting due to safety considerations.
- 6) Patients whose Mini-Mental State Examination (MMSE) scores were less than 24.
- 7) Patients who had medical history that did not fit to exercise, such as orthopedics diseases or cardiopulmonary dysfunction.
- 8) Patients who received education less than 6 years.
- 9) Patients who could not walk and live independently.
- 10) Patients who received brain surgery (e.g. deep brain stimulation);
- 11) Patients whose exercise length longer than 50 minutes per week.

All participants were fully informed and signed written consent forms. This study was approved by the ethic committee of Ruijin Hospital affiliated to Shanghai Jiao Tong University School of Medicine.

2. Randomization, Blinding and Follow-Up

There was no randomization adopted. Assessments were done at baseline and the three follow-ups (Nov. – Dec. 2019, Oct. - Nov. 2020 and Jun. – July 2021). We also monitored the frequency and lengths of Tai Chi exercise for each patient. Patients whose training were less than 60 minutes per time or less than twice per week were regarded as giving up training. The flow chart of recruitment and follow up was shown in Part II.

PD patients who did not receive Tai Chi training were matched to Tai Chi training PD patients with similar age, sex, disease duration and initial Hoehn - Yahr staging by propensity score matching methods. They also received evaluation at baseline and three follow-ups (Nov. – Dec. 2019, Oct. - Nov. 2020 and Jun. – July 2021).

Since this is an interventional study of movement, we cannot perform the blinding on patients. Thus, the assessors and the statisticians were blinded to study design. The ethic committee monitored the whole process of blinding. Patients were demanded not to tell their group assignments to the assessors.

3. Exercise Interventions and Quality Control

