5.1 Primary Outcome

The primary outcome was the annual change of UPDRS total score measured in “ON” state at three follow-ups.

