5.2 Secondary Outcomes

The secondary outcomes were annual change of the following indicators except the need of increasing antiparkinsonian therapies which were analyzed by survival analysis:

- (1) the change of LEDD⁴
- (2) the need of increasing antiparkinsonian therapies, including both the need of increasing antiparkinsonian drugs and the need of surgery, such as DBS or lesion surgery.
- (3) Motor evaluations: UPDRS part III as overall motor evaluations; TUG and BBS.
- (4) Other non-motor symptoms, including autonomic function, mood, sleep and cognition, assessed by rating scales.
- (5) Quality of life: PDQ-39;
- (6) the difference of prevalence of complications (dyskinesia, on-off phenomenon, dystonia, PD-MCI, hallucinations, restless legs syndrome).

NOTE: We consider the following aspects as the evidences for delaying disease progression:

- (1) the annual change of UPDRS total score;
- (2) the annual change of LEDD;
- (3) the need of increasing antiparkinsonian therapies.

6. Statistical Analysis

R (version 3.5.1) and RStudio (version 1.1463) were used to perform statistical analysis.

Packages stats (version 3.5.1), base (version 3.5.1), spinds (version 2.2.0), lars (version 1.2), nlme (version 3.1-145), plyr (version 1.8.5), PGEE (version 1.5), ggplot2 (version 3.2.1), survival (version 2.43-3) and survminer (version 0.4.3) were introduced into statistical analysis. Figures were plotted in Prism 9 (version 9.3.1, San Diego, CA).

All analysis about primary and secondary outcomes were conducted on an intention-to-treat basis. Analysis of variance (ANOVA) were used in comparing at numerical demographic information. Pearson Chisq-Square test or Fisher test were used in analysis at categorical demographic information. Shapiro-Wilk normality test was used to assess the normality of variables. Independent-sample t-tests (with 95% confidence intervals) were used to compare group means. Data were presented in the way of between-group differences. The longitudinal effects of self-changes were calculated using repeated measures ANOVA.

We built a cohort which started enrollment since 2016, then more patients were enrolled gradually into another 4 classes (2nd Class: start from Nov. 2016; 3rd Class: start from Mar. 2017; 4th Class: start from Sept. 2017; 5th Class: start from Jan. 2018). All the patients in those 5 classes were trained continually and has been received assessment in the follow-up of 2019, the follow-up of 2020 and the follow-up of 2021.

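### No UPDRS is scheduled between baseline and Nov–Dec 2019 and no missing-data method is stated, so patients lost for good in that gap drop out of an analysis called intention-to-treat

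*Combined protocol and SAP*

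**What the plan says.** Section 2 gives the Tai Chi schedule: "Assessments were done at baseline and the three follow-ups (Nov. – Dec. 2019, Oct. - Nov. 2020 and Jun. – July 2021". Controls follow the same pattern: "They also received evaluation at baseline and three follow-ups". Between visits, the only monitoring described is of how often and how long patients train.

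Baseline is tied to class entry: "Each participant was assessed before they joined the Tai Chi class". The Overview says that "PD patients were enrolled into 5 Tai Chi classes which began at different timepoints from Jan. 2016 to Jan. 2019". Section 6 says only that enrolment began in 2016 and then dates the other four classes: "2nd Class: start from Nov. 2016; 3rd Class: start from Mar. 2017; 4th Class: start from Sept. 2017; 5th Class: start from Jan. 2018". The two sections therefore disagree on the last class.

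Section 5.1 states: "The primary outcome was the annual change of UPDRS total score measured in “ON” state at three follow-ups". Section 6 models the change from baseline to each follow-up, with the change in LEDD as a covariate, and states: "All analysis about primary and secondary outcomes were conducted on an intention-to-treat basis". It does not define the intention-to-treat set and gives no rule for missing scores.

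Two rules concern patients who train too little. Section 2 classes those below a training threshold as having given up training, without saying that their assessments end. Section 3.1 excludes those with attendance below 75%, without saying whether from the class, the study or the analysis. Section 6 also describes all class patients as having trained continually and been assessed in 2019, 2020 and 2021.

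**The concern.** An annual change needs at least one post-baseline score. A patient who leaves for good before November 2019 has none, and has no scheduled follow-up LEDD for the covariate either. With no missing-data method stated, an analysis of observed change leaves that patient out, and the result then describes those who stayed until at least the first follow-up.

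This matters more than usual because the groups were not randomised. Their comparability rests on matching at baseline, and later loss related to progression can erode it. A patient who worsens may find it harder to attend. Only one arm has a twice-weekly class to leave and an attendance rule to fall foul of, so unequal loss is plausible. If faster progressors were lost more often from the Tai Chi arm, Tai Chi would look better on the outcome used to claim slower progression.

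**Working it through.** The plan states no sample size, loss rate or effect size, so there is no figure of its own to reproduce.

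**1. Length of the gap.** Months from class start to Nov–Dec 2019 = 12 × (difference in years) + (difference in months). For class 1: 12 × 3 + 10 = 46 to November and 47 to December. The last column divides the midpoint of the gap by the midpoint of the time to Jun–Jul 2021; for class 1, 46.5 / 65.5 = 71%.

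| Class | Start (source) | Gap, months | Share of time to last follow-up |
|---|---|---|---|
| 1 | Jan 2016 (Overview) | 46–47 | 71% |
| 2 | Nov 2016 (Section 6) | 36–37 | 66% |
| 3 | Mar 2017 (Section 6) | 32–33 | 63% |
| 4 | Sept 2017 (Section 6) | 26–27 | 58% |
| 5 | Jan 2018 (Section 6) | 22–23 | 54% |
| 5, alternative | Jan 2019 (Overview) | 10–11 | 36% |

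Control baselines are not dated, so these figures apply to the Tai Chi classes only.

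**2. Who lacks a primary outcome value.**
- Stops training but attends any follow-up: has a value, unless the 75% rule removes the patient from the analysis.
- Misses 2019 but attends 2020 or 2021: has a value.
- Leaves before Nov–Dec 2019 and is never seen again: has a baseline only.

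Only the third group is affected by the schedule itself. The need for increased therapy is analysed by survival methods, where such a patient could in principle be censored.

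**3. Illustration of loss (assumed rates).** Share lost before the first follow-up = 1 − (1 − r)^(gap in months / 12), where r is a constant annual loss and the gap is taken at its midpoint. For class 1 at r = 0.05: 1 − 0.95^(46.5/12) = 18%.

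| Assumed r | Class 1 (46.5 months) | Class 5, Jan 2018 (22.5) | Class 5, Jan 2019 (10.5) | Mean of five equal classes, class 5 in 2018 / 2019 |
|---|---|---|---|---|
| 3% | 11% | 6% | 3% | 8% / 7% |
| 5% | 18% | 9% | 4% | 13% / 12% |
| 10% | 34% | 18% | 9% | 25% / 23% |

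Equal class size is also an assumption.

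**4. Illustration of bias (assumed inputs).** If a share p of an arm is lost and those patients progress d points a year faster than those who stay, the mean among stayers lies p × d below the mean of the whole arm. The between-arm difference then shifts by (difference in p) × d. With p = 0.20 and 0.10, and d = 2 in both arms: (0.20 − 0.10) × 2 = 0.2 points a year, in favour of the arm that loses more. None of these inputs comes from the documents.

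**The case against.** The strongest reply is that visit spacing is a design choice, and that a long gap does not in itself breach intention-to-treat. Much of this stands. A reader might infer that anyone who stops training before late 2019 has no outcome. The documents do not say so: such a patient can be assessed later and analysed in the group they entered.

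A reader might also infer that no analysis could include early leavers. That is too strong. Their baseline score and covariates exist, and imputation, or a longitudinal model that retains the baseline, could keep them under untestable assumptions. Section 6 lists packages that can fit longitudinal models. What is missing is a stated method. Even a good one has no progression data from these particular patients, which is why collecting an exit score is worth more.

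Section 6's description of all class patients as assessed three times can be read either way: nobody was lost, or only completers are being described. The flow chart that might settle this is not in the text available, and its absence is not counted against the plan.

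The harm is also unproven. The loss rates and the 0.2 points a year are assumed, controls can leave too, and the text does not show which arm loses more. Finally, follow-up ended in mid-2021, so exit visits may no longer be possible. That limits the first part of the fix but not the reporting and analysis parts.

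**Conclusion.** The point holds in a limited form. No UPDRS is scheduled in either arm between baseline and Nov–Dec 2019. In the Tai Chi classes the gap is about 26 to 47 months for classes 1 to 4, and 22 to 23 or 10 to 11 months for class 5, depending on which start date is right. A blanket statement that every class waits two to four years is therefore not supported.

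Because no missing-data method is given, patients lost in the gap and never seen again drop out of the analysis that Section 6 calls intention-to-treat. The 75% attendance exclusion in Section 3.1 is potentially the more direct conflict: if it applies to the analysis, it contradicts the intention-to-treat statement whatever the visit schedule.

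The size and direction of any bias are unknown. The documents do not support a conclusion that the Tai Chi result is biased, only that the plan leaves this route to bias open and claims more than the schedule and the stated analysis secure.

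**What to change.** 1. In both arms, when a patient says they will not return, take a dated UPDRS total, Hoehn–Yahr stage and LEDD with the existing raters. Analyse these in a longitudinal model with actual time since baseline that keeps patients who have only a baseline score. Do not divide a short-interval change by time: an exit score at 3 months would have its error multiplied by 12 / 3 = 4.
2. Invite patients who stop training or fall below 75% attendance to all three follow-ups, and analyse them in the group they entered. Define the intention-to-treat set, and state what the 75% rule excludes patients from.
3. Where exit visits are no longer possible, extract dated LEDD, therapy increases and DBS from clinic records. This does not recover UPDRS, so also report per arm the number with a baseline only, run a sensitivity analysis for missing UPDRS in which leavers progress faster, and restrict the intention-to-treat claim to what the data support.
4. Reconcile the class 5 start date between the Overview (window to January 2019) and Section 6 ("5th Class: start from Jan. 2018").

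The cost is one short assessment per leaver, some chart extraction and one extra analysis. Exit values will fall at irregular times, and recovery will be incomplete because some patients will not return.

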3.1 Tai Chi

As for Tai Chi training, standardized Tai Chi was taught by professional Tai Chi coaches from Sino Taiji of Fuxing International in classes: *Qishi* (“Starting Posture”), *Shangsanbu* (“Twist Step”), *Yema Fenzong* (“Part the Wild Horse's Mane on Both Side”), *Jingang Daozhui* (“Buddha’s warrior attendant pounds mortar”), *Shoushi* (“Closing Posture”). Patients participated in this class were trained, twice a week, 60 min per time. PD patients whose attendance rate less than 75% were excluded. The detailed Tai Chi protocols are referenced as our previous work ³.

5.1 Primary Outcome

The primary outcome was the annual change of UPDRS total score measured in “ON” state at three follow-ups.

5.2 Secondary Outcomes

The secondary outcomes were annual change of the following indicators except the need of increasing antiparkinsonian therapies which were analyzed by survival analysis:

- (1) the change of LEDD⁴
- (2) the need of increasing antiparkinsonian therapies, including both the need of increasing antiparkinsonian drugs and the need of surgery, such as DBS or lesion surgery.
- (3) Motor evaluations: UPDRS part III as overall motor evaluations; TUG and BBS.
- (4) Other non-motor symptoms, including autonomic function, mood, sleep and cognition, assessed by rating scales.
- (5) Quality of life: PDQ-39;
- (6) the difference of prevalence of complications (dyskinesia, on-off phenomenon, dystonia, PD-MCI, hallucinations, restless legs syndrome).

NOTE: We consider the following aspects as the evidences for delaying disease progression:

- (1) the annual change of UPDRS total score;
- (2) the annual change of LEDD;
- (3) the need of increasing antiparkinsonian therapies.

6. Statistical Analysis

R (version 3.5.1) and RStudio (version 1.1463) were used to perform statistical analysis.

Packages stats (version 3.5.1), base (version 3.5.1), spinds (version 2.2.0), lars (version 1.2), nlme (version 3.1-145), plyr (version 1.8.5), PGEE (version 1.5), ggplot2 (version 3.2.1), survival (version 2.43-3) and survminer (version 0.4.3) were introduced into statistical analysis. Figures were plotted in Prism 9 (version 9.3.1, San Diego, CA).

All analysis about primary and secondary outcomes were conducted on an intention-to-treat basis. Analysis of variance (ANOVA) were used in comparing at numerical demographic information. Pearson Chisq-Square test or Fisher test were used in analysis at categorical demographic information. Shapiro-Wilk normality test was used to assess the normality of variables. Independent-sample t-tests (with 95% confidence intervals) were used to compare group means. Data were presented in the way of between-group differences. The longitudinal effects of self-changes were calculated using repeated measures ANOVA.

We built a cohort which started enrollment since 2016, then more patients were enrolled gradually into another 4 classes (2nd Class: start from Nov. 2016; 3rd Class: start from Mar. 2017; 4th Class: start from Sept. 2017; 5th Class: start from Jan. 2018). All the patients in those 5 classes were trained continually and has been received assessment in the follow-up of 2019, the follow-up of 2020 and the follow-up of 2021.

We set the rate of UPDRS total score change (per year) as the primary outcome. As for the secondary outcomes, UPDRS part III, other motor evaluations (TUG and BBS), evaluations of non-motor symptoms (autonomic function, mood, sleep, and cognition, assessed by rating scales), quality of life evaluated by PDQ-39, the change of LEDD, and the difference of prevalence of complications (dyskinesia, on-off phenomenon, dystonia, PD-MCI, hallucinations, restless legs syndrome). We also observed the need for increasing antiparkinsonian therapy, including increasing antiparkinsonian drugs, and deep brain stimulation (DBS). LEDD of patients who received DBS were not taken into account.

We make the comparisons between the patients who received Tai Chi training and patients who did not receive Tai Chi training as controls. Analyses of the adjusted means of change from baseline to each follow-up in rating scales were done with logarithmic linear model of covariance that included the following fixed effects: treatment group

(Tai Chi = 1, control group = 0), months in this trial, the changed amount of LEDD and baseline Hoehn-Yahr score. Years of education were also included when analyzing PDCRS. We calculated the *p* value with the bootstrap method for resampling 1000 times. To demonstrate the results, mean change with its 95% confidential intervals (CIs) was introduced. Kaplan Meier plot with table of number at risk was introduced. Bonferroni correction was introduced.

7. Safety Reporting: Adverse events (AEs) and serious adverse events (SAEs)

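### The repeated measures ANOVA of within-patient change treats each follow-up as one common time point, although time since class start at the first follow-up runs from 22 to 47 months in the Tai Chi arm

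*Combined protocol and SAP*

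**What the plan says.** Section 6 (Statistical Analysis) assigns within-patient change to one method: "The longitudinal effects of self-changes were calculated using repeated measures ANOVA". It does not say how time is coded, whether the response is a raw score or an annualised change, what covariance structure is assumed, or what happens when a visit is missed.

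The visit schedule is set by the calendar. The Overview states: "We performed three times of follow-up in Nov. – Dec. 2019, Oct. - Nov. 2020 and Jun. – July 2021". Section 2 gives the same windows for both groups.

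Baseline is set by enrolment. The Overview says "Each participant was assessed before they joined the Tai Chi class" and "PD patients were enrolled into 5 Tai Chi classes which began at different timepoints from Jan. 2016 to Jan. 2019". Section 6 says "We built a cohort which started enrollment since 2016" and lists the later classes as starting in November 2016, March 2017, September 2017 and, finally, "5th Class: start from Jan. 2018". The Overview and Section 6 thus differ by a year on the last class.

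Time is handled elsewhere in the plan. Section 5.1 defines the primary outcome as an annual change, and the between-group covariance model in Section 6 carries a fixed effect for time in the trial.

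**The concern.** With staggered entry and common calendar visits, visit number does not measure time since baseline. A repeated measures ANOVA with visit as the within-patient factor puts a patient seen about two years after baseline and one seen about four years after baseline in the same level. The estimated change from baseline to a visit is then an average over different lengths of follow-up, weighted by how many patients came from each class. It describes no particular duration, and another class mix would give another answer even if every patient progressed at the same rate.

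What is at stake is the meaning of the within-patient results. In a study of slow progression over years, they should be readable on a true time axis.

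**Working it through.** **Inputs.** Follow-up windows: November-December 2019, October-November 2020, June-July 2021 (Overview, Section 2). Class starts: January 2016 for class 1 (Overview; Section 6 gives only the year), and November 2016, March 2017, September 2017 and January 2018 for classes 2 to 5 (Section 6). Alternative last start: January 2019 (Overview). Class start stands in for baseline, because the assessment was made before joining and the gap is not stated. The plan gives no figure of its own to reproduce.

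**Formula.** Months = 12 × (difference in years) + (difference in calendar months). For class 1 at follow-up 1: November 2019 minus January 2016 = 12 × 3 + 10 = 46, and December gives 47.

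| Class start | Follow-up 1 | Follow-up 2 | Follow-up 3 |
|---|---|---|---|
| Jan 2016 | 46-47 | 57-58 | 65-66 |
| Nov 2016 | 36-37 | 47-48 | 55-56 |
| Mar 2017 | 32-33 | 43-44 | 51-52 |
| Sep 2017 | 26-27 | 37-38 | 45-46 |
| Jan 2018 | 22-23 | 33-34 | 41-42 |
| Jan 2019 (Overview date for the last class) | 10-11 | 21-22 | 29-30 |

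**Spread within one visit level.** With the Section 6 date for the last class, the ranges are 22-47, 33-58 and 41-66 months. The ratios of longest to shortest are 47/22 = 2.14, 58/33 = 1.76 and 66/41 = 1.61. With the Overview date, the ranges are 10-47, 21-58 and 29-66 months. Classes 2 to 5 alone, which need no date from the Overview, already span 22-37 months at follow-up 1.

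**Order.** Class 5 at its last follow-up (41-42 months) is earlier after baseline than class 1 at its first (46-47 months). Visit order does not preserve time order across patients.

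**What this does to a visit mean.** The plan gives no progression rate, so a constant rate, the same for everyone, is assumed. Raw change at follow-up 1 is then rate × months/12:

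| Assumed points per year | At 22 months | At 47 months |
|---|---|---|
| 1 | 1.83 | 3.92 |
| 2 | 3.67 | 7.83 |
| 3 | 5.50 | 11.75 |
| 5 | 9.17 | 19.58 |

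At 3 points per year, if a quarter of patients were at 47 months and the rest at 22, the mean change would be 0.25 × 11.75 + 0.75 × 5.50 = 7.06. With three quarters at 47 months it would be 0.75 × 11.75 + 0.25 × 5.50 = 10.19. The progression rate is identical in both cases; only the mix differs.

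**Where the effect enters.** The gaps between follow-ups, 10-12 and then 7-9 months, are common to all classes because the windows are shared. Under constant progression the mix therefore distorts the contrasts with baseline, not those between follow-ups.

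**The case against.** The strongest reply is that time is already handled where it matters most. The primary outcome is a yearly rate, most secondary outcomes are defined as annual changes, and the between-group model adjusts for time in the trial. This stands. A reader might infer from the ANOVA sentence that the primary comparison is distorted by unequal follow-up; the documents do not support that, because the sentence concerns within-patient change only.

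It can also be said that the ANOVA may have been run on annualised values. That would reduce the problem without removing it: an error of given size in the change score, divided by 22 rather than 47 months, gives an error in the rate 47/22 = 2.14 times as large, still within one visit level. Nor does the listing of the nlme package show that a mixed model was used, since none is described.

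Two further inferences are tempting. One is that patients with a missed visit are dropped. Complete-case deletion belongs to the classical form of the method, but the plan does not state it, and Section 6 says that all patients in the five classes were assessed in 2019, 2020 and 2021. What can be said is that no rule for missed visits is given. The other is that within-arm trajectories form part of the evidence for delayed progression. The note in Section 5.2 lists that evidence as annual change in UPDRS total, annual change in LEDD and the need for increased therapy; within-arm trajectories are not on the list.

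Unequal visit spacing does not by itself breach sphericity, and corrections exist, so the point does not rest on that.

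**Conclusion.** The concern holds for the within-patient analysis. In its standard form, the named method pools times since class start that differ by up to 25 months (47 − 22) at each follow-up, or by up to 37 months (47 − 10) if the last class began in January 2019. Changes from baseline by visit then depend on class mix and do not refer to a defined duration. This is more than missing detail, because a better-suited method is available at little cost.

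The conclusion rests on three assumptions: that visit enters as a factor, as is standard and as nothing in the plan contradicts; that class start approximates baseline; and that the first class began in January 2016. It is shown for the Tai Chi arm only, because control baseline dates are not given. It merits correction but does not call the primary between-group comparison into question.

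**What to change.** Replace the repeated measures ANOVA with a linear mixed model for each scale score:

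- time as actual months from each patient's own baseline assessment, entered as a continuous variable;
- fixed effects for arm, time and arm-by-time, with a random intercept and a random slope per patient;
- all available visits, with this stated as the rule for missed visits;
- within-arm slopes reported with 95% confidence intervals.

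Label any arm-by-time contrast from this model as supportive of the planned between-group model, so that it does not become a second main analysis. Check linearity, because no assessment is planned between baseline and the first follow-up window.

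Reconcile the last class start (January 2018 in Section 6, January 2019 in the Overview), and report baseline dates or follow-up times for the controls.

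The cost is a small re-analysis using assessment dates, revised wording in Section 6, and reliance on a linearity assumption. No new assessments are needed, and nlme, which fits such models, is already among the listed packages.

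### The primary outcome is UPDRS change per year, but the only adjusted model in Section 6 is written for change to each follow-up with an unexplained log, so the primary estimate and p value are not fixed

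*Combined protocol and SAP*

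**What the plan says.** Section 5.1 states: "The primary outcome was the annual change of UPDRS total score", rated in the ON state at three follow-ups. Section 6 repeats the definition: "We set the rate of UPDRS total score change (per year) as the primary outcome". Section 5.2 puts most secondary outcomes on the same footing: "The secondary outcomes were annual change of the following indicators".

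The adjusted comparison of Tai Chi with control is in Section 6: "Analyses of the adjusted means of change from baseline to each follow-up in rating scales were done with logarithmic linear model of covariance". Its fixed effects are treatment group plus "months in this trial, the changed amount of LEDD and baseline Hoehn-Yahr score". The p value comes from a bootstrap with 1000 resamples, results are shown as mean change with a 95% CI, and a Bonferroni correction is mentioned without naming the tests it covers.

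Section 6 also lists independent-sample t-tests for group means, presentation as between-group differences, and repeated measures ANOVA for within-patient change. The one rule that mentions the primary outcome by name sets the population, not the test: "All analysis about primary and secondary outcomes were conducted on an intention-to-treat basis".

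On LEDD, the note in Section 5.2 counts "the annual change of LEDD" among three signs of delayed progression, and Section 6 adds: "LEDD of patients who received DBS were not taken into account".

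**The concern.** The outcome and the model describe different quantities. A rate per year is not a change up to a visit when patients joined in different years and were all assessed in the same calendar windows. Entering months as a main effect adjusts for length of follow-up, but it does not convert the group coefficient into points per year. That would take a group-by-time term or an annualised response, and the model sentence mentions neither.

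The word logarithmic adds a second uncertainty, because the text does not say whether the score, the change, a ratio or a covariate is logged. With three follow-ups, no rule for combining them and no Bonferroni family, Section 6 does not fix which number and which p value are the primary result. This matters more than usual here because the cohort is not randomised, and pre-specification is one of its main safeguards against selecting a result.

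A related problem is the covariate for change in LEDD. It is measured after baseline and is also an outcome, so adjusting for it changes the question asked.

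**Working it through.** The plan gives no sample size, effect size, SD or alpha, so there is no stated figure to reproduce. The check compares what the model would estimate with what Section 5.1 defines.

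**Inputs from the documents.** Class starts in Section 6: Nov 2016, Mar 2017, Sept 2017 and Jan 2018. Class 1 is dated only 2016 there; Jan 2016 is taken from the Overview. Follow-up windows: Nov–Dec 2019, Oct–Nov 2020, Jun–July 2021.

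**Assumptions.** Five classes of equal size; controls on the same dates; assessment at mid-window; constant rates of 3 points/year (control) and 2 points/year (Tai Chi), so the true difference is -1 point/year.

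**Months from class start to follow-up**

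| Follow-up | Class 1 | 2 | 3 | 4 | 5 | Mean months | Mean years |
|---|---|---|---|---|---|---|---|
| 1 | 47 | 37 | 33 | 27 | 23 | 167/5 = 33.4 | 2.78 |
| 2 | 58 | 48 | 44 | 38 | 34 | 222/5 = 44.4 | 3.70 |
| 3 | 66 | 56 | 52 | 46 | 42 | 262/5 = 52.4 | 4.37 |

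**Reading 1: change, untransformed.** Change = rate × years. With the same timing in both groups, months and group are uncorrelated, so the group coefficient in a fit on group + months is (2 − 3) × mean years: **-2.78, -3.70 and -4.37 points**. Pooling the three visits equally gives -3.62.
- Counting instead to the first month of each window gives -2.70, -3.62 and -4.28.
- With a last class start of Jan 2019, as the Overview has it, class 5 has 11, 22 and 30 months. The means become 155/5 = 31, 42 and 50 months, and the coefficients -2.58, -3.50 and -4.17.
- With a different class mix in each group (5,000 noise-free random designs, 100 per group), 95% of coefficients lay between -3.22 and -2.34, -4.12 and -3.28, and -4.76 and -3.95. No sign was wrong, and with equal rates the estimate was zero.

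**Reading 2: score on a log scale.** The group effect becomes a ratio, (B + 2y)/(B + 3y), for baseline B and mean years y. For B = 25 at follow-up 1: (25 + 5.57)/(25 + 8.35) = 30.57/33.35 = 0.92; at follow-ups 2 and 3 it is 0.90 and 0.89. At follow-up 1 it is 0.88 for B = 15 and 0.94 for B = 40. One annual difference therefore maps to several ratios, and none is the between-group difference that Section 6 says will be shown.

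**Reading 3: annualised change, untransformed.** Change/years is 2 or 3 for every patient, so the group term is -1.00 at each follow-up. This is the stated primary quantity.

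**From estimate to p value.** The bootstrap sentence says how a p value is obtained, but not for which coefficient or visit. The documents do not say whether there is one primary comparison or three, or whether Bonferroni covers visits, outcomes or both.

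**LEDD and DBS.** If a DBS patient's LEDD is set aside, change in LEDD has no stated value for that patient in the adjusted model. A complete-case fit may then omit the patient, contrary to the intention-to-treat sentence.

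**The case against.** The strongest reply is that the plan can be read sensibly. UPDRS is one of the listed rating scales, and the model follows closely on the primary-outcome definition, so it was presumably meant to cover UPDRS. Since the document repeatedly speaks of annual change, the response may well have been annualised. That is a fair reading and it would give the right quantity. What stands against it is that the model sentence names a different response, and nothing says how three annualised values become one result.

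Several stronger inferences are tempting, and the documents do not support them.
- *That the primary outcome has no available test.* The adjusted model and the t-test could each serve; neither is designated.
- *That the untransformed model gives a wrong answer on whether Tai Chi works.* Under constant rates its sign and null are right, with balanced or unbalanced timing. A cumulative difference is a legitimate quantity in other units.
- *That patients with zero or negative change are lost to the log.* This follows only if the change score itself is logged, which is not stated.
- *That the type I error rate is inflated.* Three visits each tested at an assumed 5% would give 8–13% false positives if uncorrected, but Bonferroni is named; if it covers the three, the figure is 3.0–4.5%.
- *That significance is arbitrary.* With 75–150 per group and assumed SDs, tests at the three visits disagreed on p < 0.05 in 18–41% of simulated trials. That is largely ordinary power variation; at an assumed 300 per group it was about 2%.
- *That DBS patients are dropped.* The text leaves this open.

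**Conclusion.** The concern holds as a mismatch between the stated primary quantity and the only adjusted model, together with an unfixed primary result. Read literally and untransformed, the model's group term exceeds the annual difference by a factor equal to mean years of follow-up: about 2.8, 3.7 and 4.4 on the Section 6 dates, or 2.6, 3.5 and 4.2 with the Overview's last start date. These factors rest on equal classes, matched timing and constant rates. The textual mismatch rests on none of these. On a log scale the result would be a ratio; on an annualised reading there would be no discrepancy in size.

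This should be fixed. It is more than missing detail, because following the sentence as written does not estimate the primary outcome. It does not by itself show that the direction or the significance of any reported result is wrong.

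**What to change.** Make the primary analysis one untransformed model of the per-year rate, in either of two forms.
- A linear mixed model on UPDRS total with years since each patient's own baseline, group, group × years, baseline Hoehn-Yahr, and random intercept and slope. The package nlme is already listed.
- The adjusted model on annualised change, with a stated rule that combines the three follow-ups.

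Then:
- Report one group difference in points per year, with its 95% CI, as the single primary test.
- Keep the bootstrap p value, resampling whole patients so that their repeated assessments stay together.
- State which tests the Bonferroni family contains.
- Report the primary model with and without change in LEDD, and say that the two answer different questions. State how DBS patients enter the LEDD-adjusted fit, so that they are not lost despite intention-to-treat.
- Reconcile the last class start (Jan 2019 in the Overview, Jan 2018 in Section 6), because it sets the time variable.

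The cost is plan wording and a re-run on collected data. Follow-up ended in July 2021, so any re-analysis is post hoc; label it so and show it beside the original. A slope model also cannot separate a one-off shift from slower progression: under assumed variances, a single 3-point improvement would appear as about -0.73 points/year. Annualised change shares the limitation (-1.15, -0.84 and -0.70 at the three visits). A sensitivity analysis with a post-baseline group step term separates the two, but its standard error is about 2.0 to 2.2 times larger under those variances.
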